#### 6.1.1 Dose Modifications and Delays

In the event of a subject forgetting to take drug with their largest meal that day, they can take the study drug later in the day and return to their regular schedule the next day. In the event of a subject not taking drug on a given day, he or she should not take more than the daily dose on the following day.

Temporary interruptions of study medication are allowed. Interruptions of study medication for longer than 14 days need approval of the sponsor whenever possible. In the event of a subject experiencing intolerable adverse events considered related to study medication by the investigator, the investigator should consider decreasing the dose to one tablet once daily before interrupting or permanently discontinuing study medication.

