6.3.6 Treatment Compliance

Accountability and subject compliance will be assessed by maintaining adequate drug dispensing and return records. Subjects will be asked to return all used and unused drug supply containers at each visit as a measure of compliance.

An overall compliance calculation will be performed using the study administration intake recorded. Compliance for the whole study is derived as follows:

$$\text{Compliance} = \frac{\text{\# days subject took study medication}}{\text{\# days in the study}} \times 100$$

days in the study = Date subject completed the study - date of randomization + 1.

Total time on study medication = Date of treatment last dose - date of treatment first dose + 1.

days subject took study medication (duration of treatment exposure) = Total time on study medication - the sum of all interruption durations for each record on the *Treatment Inter/ Disc* Form of the eCRF. It should be noted that only interruptions over 7 days are captured.

Subjects who died with no report of study drug discontinuation will be considered as discontinuing drug on date of death and date of treatment last dose will be imputed as date of death.

Compliance will be summarized by treatment arm using descriptive statistics.

Compliance will also be categorized as follow: < 80% or [80%-100%] and summarized accordingly using frequencies and percentages, by treatment arm, for the subjects of the ITT population.

Compliance results will be listed.

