6.4.5.4 Analysis Based on Exposure to Study Treatment

Subjects who were off study treatment for an extended period of time may have a different risk profile as compared to the ITT population and two additional analyses will be performed to investigate the effect of exposure to study treatment.

- 1) Excluding events occurring 14 days after last dose of study treatment in subjects who discontinued study treatment prematurely

The time from randomization to first occurrence of any component of the composite endpoint of CV death, resuscitated cardiac arrest, non-fatal MI or non-fatal stroke (primary endpoint) will be calculated as number of days between randomization and event in subjects with an event and event-free subjects will be censored at the date they were last known to be event free (as for the primary analysis). However, in subjects who discontinued treatment prematurely (i.e. who reported a study treatment discontinuation on the *Treatment Inter/ Disc* Form of the eCRF), any event occurring 14 days or more after date of last dose will not count as an event. The analysis will be conducted on all randomized subjects (no subject excluded) using the same model as described in section 6.4.1.

- 2) Excluding subjects who discontinued study treatment prematurely and who had their first event at least 14 days after last dose of study treatment

The time from randomization to first occurrence of any component of the composite endpoint of CV death, resuscitated cardiac arrest, non-fatal MI or non-fatal stroke (primary endpoint) will be calculated as number of days between randomization and event in subjects with an event and event-free subjects will be censored at the date they were last known to be event free (as for the primary analysis). However, subjects who discontinued treatment prematurely (i.e. who reported a study treatment discontinuation on the *Treatment Inter/ Disc* Form of the eCRF) and who had a first event occurring 14 days or more after last dose will be excluded. The analysis will not be conducted on all randomized subjects since some would be excluded but it will use the same model as described in section 6.4.1.

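### The two exposure analyses in SAP 6.4.5.4 ignore treatment interruptions, so whether an event 14 days or more off drug counts can depend on what happens after it

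*SAP*

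**What the plan says.** SAP 6.4.5.4 gives its reason for looking at exposure as follows: "Subjects who were off study treatment for an extended period of time may have a different risk profile as compared to the ITT population". Both analyses then use the same trigger. They act only on subjects "who reported a study treatment discontinuation on the" Treatment Inter/Disc form. In the first analysis, for those subjects, "any event occurring 14 days or more after date of last dose will not count as an event". In the second, those "who had a first event occurring 14 days or more after last dose will be excluded" from the analysis. Each measures the 14 days from one date of last dose per subject. Neither mentions interruptions.

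Elsewhere the documents treat interruptions as a separate and expected state:

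- Protocol 6.1.1: "Temporary interruptions of study medication are allowed. Interruptions of study medication for longer than 14 days need approval of the sponsor whenever possible". No maximum length is set.
- SAP 6.3.6 subtracts recorded interruption durations from days on study medication, and adds: "It should be noted that only interruptions over 7 days are captured".
- SAP 6.5.1 lists interruption and discontinuation as different things and tabulates permanent discontinuations.
- SAP 6.3.6 also has a rule for deaths: "Subjects who died with no report of study drug discontinuation will be considered as discontinuing drug on date of death", with the last-dose date set to that day.

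**The concern.** The section is about time off drug, but its rule identifies only one way of being off drug. A subject in a long interruption is off drug for compliance and exposure under SAP 6.3.6. An event in that same interruption is nevertheless handled in 6.4.5.4 as if the subject were exposed, unless a discontinuation is reported with a last dose at least 14 days before the event.

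Whether a stop ends up as an interruption or a discontinuation is often settled only later, by whether drug is restarted. If the event falls between the stop and that decision, the event's label depends on the future. A myocardial infarction or stroke could plausibly influence whether a subject restarts, so the filter may be related to the outcome it is filtering.

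At stake is the reading of two supportive results. They are the only efficacy analyses in the SAP that take drug exposure into account: the protocol's per-protocol population (Protocol 8.2.2.3) is not among the datasets listed in SAP section 3. Long gaps in dosing are also a foreseeable case, since Protocol 5.3.1 and SAP 2.1 describe disruption of visits and drug supply during the pandemic.

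**Working it through.** **Background figure.** The planned event count reproduces and is not in dispute. With 1:1 allocation, a two-sided alpha of 0.05, 85% power and a hazard ratio of 0.78 (22% risk reduction, SAP 6.1), Schoenfeld's formula gives 4 × (1.960 + 1.036)² / (ln 0.78)² = 582 events.

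**Applying the rule.** Take an assumed subject whose last dose before a stop is day 100 and whose event is on day 160, so 60 days off drug. As written, the event is dropped only if (i) a discontinuation is reported and (ii) event day minus date of last dose is at least 14.

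| What happens around or after the event | Discontinuation reported? | Date of last dose | Event minus last dose | Handling in 6.4.5.4 |
|---|---|---|---|---|
| Restarts day 190, stays on drug | No | – | – | Counts |
| Restarts day 190, discontinues day 400 | Yes | 400 | −240 | Counts |
| Never restarts, discontinuation reported | Yes | 100 | 60 | Dropped (analysis 1); subject excluded (analysis 2) |
| Never restarts, interruption left open | No | – | – | Counts |
| Event is a CV death in an open interruption | No | – | – | Counts |
| Event is a CV death, discontinuation reported | Yes | 100 | 60 | Dropped; subject excluded |

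In all six rows the subject has been off drug for the same 60 days. The label differs because of what is recorded or done around or after the event. The second row shows that even a later discontinuation does not bring the event within the rule, because the single last-dose date has moved past it.

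Only events 14 days or more into an interruption are affected. Earlier ones would count under the SAP's own window anyway.

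**Size.** The documents give no frequency or length of interruptions, so this is an illustration. Let *s* be the share of follow-up handled as exposed that is really 14 days or more into an interruption. Assume *s* is equal in both arms, the same underlying risk on and off drug, a hazard ratio of 0.78 on drug and 1.0 off drug. Then

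HR = (1 − s) × 0.78 + s × 1.0

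| s | HR | Shift in log HR, ln(HR/0.78) | Shift ÷ standard error |
|---|---|---|---|
| 1% | 0.782 | 0.003 | 0.03 |
| 3% | 0.787 | 0.008 | 0.10 |
| 5% | 0.791 | 0.014 | 0.17 |
| 10% | 0.802 | 0.028 | 0.34 |

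The standard error of the log hazard ratio is taken as 2/√582 = 0.083. These analyses would have somewhat fewer than 582 events, so the true ratios in the last column are slightly smaller. For scale, 1% and 5% of 582 are about 6 and 29 events.

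**The case against.** The strongest reply is that this is minor. SAP 6.4.6 says analyses outside the primary and secondary tests are interpreted descriptively. Interruptions beyond 14 days, the same length as the SAP's window, are what Protocol 6.1.1 refers to the sponsor. Even at an assumed 5% the hazard ratio moves by about one sixth of a standard error. All of this stands and limits the weight of the point. It does not remove it: the sponsor check applies only where possible and sets no cap, and the rule still labels identical exposure in opposite ways, against the section's stated aim.

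A reader might also infer more than the documents support:

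- *That fatal events in interruptions are always kept and non-fatal ones dropped.* Both depend on whether a discontinuation is reported and with which last-dose date. The table shows a death dropped and a non-fatal event kept. How the form converts an unresumed interruption into a discontinuation is not visible here, so differential filtering by component is possible but not established.
- *That the death rule in SAP 6.3.6 is the cause.* It is not. A death with no reported discontinuation is never reached by 6.4.5.4, so it counts whatever last-dose date is imputed. The imputation matters only once the 14-day rule is extended to such subjects.
- *That never-dosed subjects are counted as exposed.* SAP 6.4.5.4 is silent on them, and their number is shown separately under SAP 6.3.1 and 6.5.1.
- *That the analyses are unusable.* The illustrated shifts do not support that.

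**Conclusion.** The point holds as a fault of classification in two descriptive analyses. SAP 6.4.5.4 recognises time off drug only through a reported discontinuation and one last-dose date, so an event well into an interruption can be kept or dropped according to what follows it. This is also inconsistent with SAP 6.3.6, which takes interruption time out of exposure.

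The primary ITT test and the 582-event calculation are unaffected. The likely effect is small: about 0.782 to 0.791 in place of 0.78 for a 1% to 5% share. Those figures rest on an assumed share, equality between arms and no drug effect during interruptions. If interruption, restart or reporting after an event differed by arm, the estimate could move further, in either direction; the documents give nothing from which to size that. The reading also takes discontinuation in 6.4.5.4 to mean a permanent stop, as in SAP 6.5.1.

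**What to change.** In SAP 6.4.5.4, for both analyses, replace the trigger with drug status at the event date. Suggested wording: *The 14 days are measured from the last dose actually taken before the event, as derived from the Treatment Inter/Disc form, whether that stop was recorded as an interruption or as a discontinuation and whether or not study drug was later restarted. For a death during an open recorded interruption, the last dose before that interruption is used, not the date of death imputed under 6.3.6.*

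Analysis 1 then does not count any event at or beyond 14 days. Analysis 2 excludes any subject whose first event meets the same condition. All six histories in the table would be handled alike. The 7-day capture limit is finer than the 14-day window, so every relevant interruption should be on the form.

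The cost is SAP wording, modest programming and slightly fewer events in two descriptive analyses. The change relies on the form holding interruption dates, which is inferred from the recorded durations and should be confirmed against the case report form. The label would no longer depend on behaviour after the event, but it would still depend on stopping and restarting before it, so the results remain descriptive. How follow-up time off drug is treated is a separate question that this change leaves as it is.

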6.4.6 Adjustment for multiplicity

Statistical testing of the primary and secondary endpoints will be done hierarchically to control the type 1 error rate at level 0.05. This will be done by testing the primary endpoint first and to test the secondary endpoints using the Hochberg procedure only if the primary analysis results in a significant treatment effect. Other analyses will be interpreted descriptively. The process is described below.

Primary Hypotheses:

The statistical hypotheses to be tested for the primary analysis are:

$$H_0: \lambda = 1 \text{ vs. } H_A: \lambda \neq 1$$

where λ is the HR for the time to occurrence of the primary endpoint for the dalcetrapib and placebo groups.

Secondary Hypotheses:

The statistical hypotheses to be tested for the secondary analyses are:

$$H_{0:S1}: \lambda_{S1} = 1 \text{ vs. } H_{A:S1}: \lambda_{S1} \neq 1$$

$$H_{0:S2}: \lambda_{S2} = 1 \text{ vs. } H_{A:S2}: \lambda_{S2} \neq 1$$

where

λ_{s1} is the HR for time to occurrence of the first secondary endpoint (CV death, resuscitated cardiac arrest, non-fatal MI, non-fatal stroke, hospitalization for ACS [with ECG abnormalities], or unanticipated coronary revascularization)

λ_{s2} is the HR for time to occurrence of the second secondary endpoint (CV death, resuscitated cardiac arrest, non-fatal MI, non-fatal stroke, or hospitalization for new or worsening heart failure)

Primary Analysis

Reject H_0 if p-value from the stratified Cox proportional hazards model is ≤ 0.05 .

Secondary Analyses

If H_0 is not rejected, the hypotheses for the secondary endpoints will not be formally tested. If H_0 is rejected, the following rules will be applied:

1. Order the p-values from the stratified Cox proportional hazards models of the secondary null hypotheses, $H_{0:s1}$ and $H_{0:s2}$, from largest to smallest.
2. If the largest p-value is ≤ 0.05 , reject both secondary null hypotheses.
3. If the largest p-value is > 0.05 and the smallest p-value is $\leq 0.05/2 = 0.025$, reject the secondary null hypotheses corresponding to the smallest p-value.
4. Otherwise, reject none of the secondary null hypotheses $H_{0:s1}$ and $H_{0:s2}$.

6.5 Safety Analysis

All safety parameters will be summarized and presented in tables based on the ITT population.

For the evaluations of adverse events and general laboratory data described below, neither tests of hypotheses nor estimates of treatment effects will be reported, unless otherwise specified. It is, however, anticipated that in some instances there will be numerical treatment differences in the reported summary statistics that are either of interest or concern; in these instances, more extensive exploratory statistical analyses may be performed. The scope of the analyses cannot be determined a priori, but would be expected to include standard regression methods for estimating relative risks such as odds and hazard ratios.

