#### 8.2.2.2 Intent to Treat (ITT) Population

All subjects randomized will be included in the ITT population.

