#### 8.2.2.4 Safety Analysis Population

All subjects who received at least one dose of treatment will be included in the safety analysis population. Subjects will be assigned according to the true treatment received for analysis purposes.

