#### 8.2.5 Safety Analyses

All safety parameters will be summarized and presented in tables based on the safety population.

For the evaluations of adverse events and general laboratory data described below, neither tests of hypotheses nor estimates of treatment effects will be reported. It is however anticipated that in some instances there will be numerical treatment differences in the

reported summary statistics that are either of interest or concern; in these instances, more extensive exploratory statistical analyses may be performed. The scope of the analyses cannot be determined a priori; but would be expected to include standard regression methods for estimating relative risks such as odds and hazard ratios.

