1. INTRODUCTION

The purpose of this statistical analysis plan (SAP) is to present the statistical methodology that will be used for the final analysis of DalCor protocol number DAL-301. This plan also provides a description of the analyses used to produce the tables, figures, and listings that will be included in the final statistical report. This SAP is based on the protocol Version 5 dated 11FEB2021 and on the annotated case report form (CRF) version 3.1. In case of differences between the SAP and the protocol, the SAP will supersede the protocol. Any deviation to this SAP would be reported in the statistical report.

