6.3.3 Datasets Analyzed

The number of subjects in the ITT population will be summarized.

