6.5.2.1 Adverse Events

Summary statistics will be presented by treatment arm for all treatment-emergent adverse events (TEAEs) and, in addition, by intensity [Mild, Moderate, Severe, Life-Threatening] and relationship to study medication as judged by the investigator [Not Related, Related]. A treatment-emergent AE will be defined as an AE with onset date on or after the date of randomization. For subjects experiencing repeated episodes, only the most severe episode and the episode with the strongest relationship will be reported. Summary statistics will include number and incidence of events where incidence of an event within a treatment group will be determined as the simple proportion of subjects in the group experiencing the event.

Adverse events will be grouped and summarized by system organ class and preferred term as defined by the latest version of the Medical Dictionary for Regulatory Activities (MedDRA, version 19.1 or higher).

All AEs will be included in subject data listings but only treatment-emergent AEs will be summarized.

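### SAP 6.5 bases every safety table on the ITT population, where the protocol requires dosed subjects grouped by treatment received; the visible SAP gives no reason, and the numerical effect is probably small.

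*SAP*

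**What the plan says.** The protocol defines two relevant sets.

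- **ITT (8.2.2.2):** "All subjects randomized will be included in the ITT population".
- **Safety (8.2.2.4):** "All subjects who received at least one dose of treatment will be included in the safety analysis population". The section adds: "Subjects will be assigned according to the true treatment received for analysis purposes".

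Protocol 8.2.5 then uses the second set: "All safety parameters will be summarized and presented in tables based on the safety population".

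SAP 6.5 has the same sentence with the population exchanged: "All safety parameters will be summarized and presented in tables based on the ITT population". The SAP's table of contents lists only an ITT and an Intent-to-Diagnose set under section 3. SAP 6.3.3 counts only one of them: "The number of subjects in the ITT population will be summarized". SAP section 1 settles which document governs: "In case of differences between the SAP and the protocol, the SAP will supersede the protocol".

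SAP 6.5.2.1 ties the counting of events to randomization, not to dosing: "A treatment-emergent AE will be defined as an AE with onset date on or after the date of randomization".

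The SAP also foresees the subjects for whom the two sets differ. Section 6.3.1 reports how many randomized subjects took study medication, 6.5.1 has a category for no exposure, and 6.3.2 treats receipt of the wrong treatment as a major deviation.

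**The concern.** A safety table should show what happened to people who took a drug, under the drug they took. The protocol's rule does this. Under the SAP's rule, a subject randomized to placebo who received dalcetrapib has any adverse event counted under placebo, and the reverse. An undosed subject who remains in ITT enlarges the denominator, because SAP 6.5.2.1 computes incidence as a simple proportion of the group. Any event that such a subject has after randomization also qualifies as treatment-emergent.

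Long-term safety is a stated objective in both documents, and SAP 2.2 names diabetes within it. The choice of population also reaches two safety comparisons that are modelled or tested: HbA1c by ANCOVA (SAP 6.5.3) and new-onset diabetes by a Cochran-Mantel-Haenszel test, which 6.5.5 places explicitly on ITT.

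**Working it through.** **No plan figure is at stake.** The documents give no count of undosed or wrongly treated subjects and no figure for this point. The event target does not depend on the safety set. It reproduces as 4(1.960 + 1.036)² / (ln 0.78)² = 582.

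**Inputs.** From the SAP: 6149 randomized 1:1 (sections 2.1 and 6.1), about 3,074 per arm. Everything else is assumed:

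- f = share never dosed in each arm
- w = share in each arm given the other treatment throughout
- p1, p0 = true event risks on dalcetrapib and on placebo

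**Risk difference, equal shares, undosed subjects at background risk p0.**

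- Dalcetrapib arm as randomized: (1 − f − w)p1 + (f + w)p0
- Placebo arm as randomized: (1 − w)p0 + w·p1
- Difference: (1 − f − 2w)(p1 − p0)

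If undosed subjects report no events, the arms become (1 − f − w)p1 + w·p0 and (1 − f − w)p0 + w·p1. The difference is again (1 − f − 2w)(p1 − p0).

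| f | w | Undosed per arm | Wrongly treated per arm | Share of excess risk left |
|---|---|---|---|---|
| 0.1% | 0 | 3 | 0 | 99.9% |
| 0.5% | 0.1% | 15 | 3 | 99.3% |
| 1% | 0.1% | 31 | 3 | 98.8% |
| 2% | 0.1% | 61 | 3 | 97.8% |

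A deliberately extreme case, f = 5% and w = 1%, leaves 93.0%.

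**Risk ratio.** Take p0 = 5% and a true ratio of 1.50 (assumed).

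- f = 1%, w = 0.1%: 1.494 with undosed subjects at background risk, 1.499 if they report no events.
- f = 2%, w = 0: 1.490 at background risk, exactly 1.500 if they report no events, because (1 − f) cancels.
- f = 0, w = 1%: 1.488. Misallocation alone lowers the ratio.

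**Unequal undosed shares.** Suppose undosed subjects report no events, true risks are 20% and 15%, and the undosed share is 0.3% on dalcetrapib and 2% on placebo (all assumed).

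- Dalcetrapib: 20% × 0.997 = 19.94%
- Placebo: 15% × 0.98 = 14.70%
- Difference: 5.24 points against a true 5.00
- Ratio: 1.356 against a true 1.333

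Here the ITT table overstates the harm.

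**The case against.** A reader might infer that ITT safety tables always hide harm. The documents do not support that. Misallocation does push toward zero, but the effect of undosed subjects depends on whether they report events and on whether their shares are equal. As shown above, the risk ratio can be unchanged, and both measures can move away from zero.

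A reader might also infer that the sponsor changed the population with no justification at all. That cannot be said. SAP 3.2 was not available for review, and Amendment 2 added to it a list of subjects excluded from ITT. Those exclusions could cover some or all undosed subjects, and the section could explain the choice. The no-exposure category in 6.5.1 suggests that some undosed subjects remain, but does not prove it.

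The case for leaving the plan alone has weight:

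- Adverse event and general laboratory tables carry no tests or effect estimates unless otherwise specified, and SAP 6.5 allows further analysis where a difference causes concern.
- The disposition count, exposure table and deviation listing let a reader gauge how many subjects are affected.
- Receiving the wrong treatment may mean a single dispensing, in which case the assumption of wrong treatment throughout overstates the effect.

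These points limit the consequences, but none of them supplies an as-treated table. The usual argument for ITT safety, that it retains events after a subject stops the drug, does not help here. Protocol 8.2.2.1 and SAP 3.1 both keep all data from any subject in a set, so the protocol's dosed population retains those events too.

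**Conclusion.** The inconsistency is real and, in the text available, unexplained. Because the SAP governs, wrongly treated subjects are counted under a treatment they did not take, and any undosed subjects left in ITT enter the denominators.

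The size is probably small. With 0.1% to 2% undosed and 0 to 0.1% wrongly treated in each arm, about 98% to 99.9% of an excess risk remains. These shares are assumptions, taken as equal between arms and with wrong treatment lasting throughout. Only the misallocation part has a fixed direction, toward no difference. The point is worth correcting because the protocol's own rule answers the safety question better and the correction is nearly free, not because a large distortion has been shown.

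**What to change.** 1. Restore the protocol's safety population in SAP section 3: at least one dose, grouped by treatment actually received. Count it in 6.3.3.
2. Use it for all of 6.5, including the HbA1c comparison (6.5.3) and the new-onset diabetes test (6.5.5).
3. In 6.5.2.1, start treatment-emergent events at first dose, so that the event window matches the population. Earlier events stay in the listings.
4. Add a rule for subjects who received both treatments. Protocol 8.2.2.4 does not cover them, so restoring its wording alone would leave them unclassified.
5. Keep the ITT tables as supportive. If the sponsor prefers ITT as the main set, state the reason and add the as-treated tables.

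**Cost:** SAP wording, one analysis flag and one classification rule. The first-dose date already enters the exposure calculation (6.3.6), and wrong treatment is already captured in the eCRF (6.3.2). Safety denominators will differ slightly from those in the efficacy tables. The sample size and event target do not change.
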